### 8.2.2. Exclusion criteria

Patients meeting any of the following criteria will not be included in the study:

- Patients without information on mortality
- Patients with ECOG performance status  $\geq 2$  (at the time of randomization for patients from COLUMBUS, during the baseline period for patients in Flatiron EHR)
- Patients with a history of or concurrent uveal or mucosal melanoma, basal cell or squamous cell carcinoma (as per trial inclusion criteria); this exclusion will also be applied to RWD patients
- For RWD patients, concurrent enrollment in a clinical trial.

### 8.3. Variables

**Table 1** provides a summary of exposure, outcome, and patient baseline characteristics that will be evaluated within the study.

**Table 1.** Key exposures, outcomes, and patient baseline characteristics in the COLUMBUS trial data and Flatiron Health EHR data

Variable	Role	Data source(s)	Operational definition
ENCO+BINI Cohort (Columbus or Flatiron)	Exposure	Columbus trial data; Flatiron EHR	Binary variable indicating whether ENCO+BINI patients are derived from the Columbus trial data vs. Flatiron EHR population
OS	Primary Outcome	Columbus trial data, Flatiron EHR	In Columbus trial data, defined as the time from the date of randomization to the date of death due to any cause; if death is not observed, patients will be censored at the date of last contact or the data analysis cut-off date (e.g., 15 September 2020), whichever occurs first  In Flatiron EHR, defined as the time from the index date to the date of death; patients without a date of death will be censored at their last known activity date (e.g., the last clinical note date) or the end of the follow-up period whichever occurs first
PFS	Exploratory Outcome	Columbus trial data, Flatiron EHR	In Columbus trial data, defined as the time from the date of randomization to the date of the first documented disease progression or death due to any cause, whichever occurred first; if a patient did not have an event at the analysis cut-off date, PFS will be censored at the date of the last adequate tumour assessment  In Flatiron EHR, defined as the time from the index date to either the date of first disease progression event or death in the absence of progression; patients without disease progression or death will be censored at the last date the

PFIZER CONFIDENTIAL

			patient could have been assessed for progression (e.g., the last clinical note date) or the end of the study period (e.g., 01 January 2022), whichever occurs first
Age at index	Baseline Characteristic / Potential Confounder	Columbus trial data; Flatiron EHR	Patient age; defined at the time of study randomization for Columbus trial data and treatment initiation for Flatiron EHR
Sex	Baseline Characteristic / Potential Confounder	Columbus trial data; Flatiron EHR	Male, Female, Intersex, and Unknown/Missing
Race	Baseline Characteristic / Potential Confounder	Columbus trial data; Flatiron EHR	Asian, Black, White, Other/Multirace, and Unknown/Missing
Ethnicity	Baseline Characteristic / Potential Confounder	Columbus trial data; Flatiron EHR	Hispanic/Latino, Non-Hispanic/Latino, and Unknown/Missing
Body mass index (BMI) at index	Baseline Characteristic / Potential Confounder	Columbus trial data; Flatiron EHR	Defined as weight (in kg) divided by squared height (in m  )
ECOG at index	Baseline Characteristic / Potential Confounder	Columbus trial data; Flatiron EHR	0, 1, Unknown/Missing; defined during the baseline period of both Columbus trial data and Flatiron EHR
Disease stage at diagnosis	Baseline Characteristic / Potential Confounder	Columbus trial data; Flatiron EHR	IIIB, IIIC, IVM1a, IVM1b, or IVM1c; defined at metastatic melanoma diagnosis for both Columbus trial data and Flatiron EHR
Lactate dehydrogenase (LDH) at index	Baseline Characteristic / Potential Confounder	Columbus trial data; Flatiron EHR	Evaluated in units per liter (U/L) and defined at trial baseline in Columbus trial and during the baseline period in Flatiron EHR
Time from diagnosis to metastatic disease	Baseline Characteristic / Potential Confounder	Columbus trial data; Flatiron EHR	Duration (in months) from melanoma diagnosis to the development of metastatic disease
Time from metastatic diagnosis to treatment initiation	Baseline Characteristic / Potential Confounder	Columbus trial data; Flatiron EHR	Duration (in months) from metastatic melanoma diagnosis to the initiation of ENCO+BINI treatment
Year of ENCO+BINI Treatment	Baseline Characteristic	Columbus trial data; Flatiron EHR	Calendar year when ENCO+BINI treatment was initiated
Prior Systemic Therapy	Baseline Characteristic / Potential Confounder	Columbus trial data; Flatiron EHR	Binary variable indicating whether patients previously received systemic therapy (e.g., prior surgery, radiotherapy, immunotherapy, or chemotherapy) before ENCO+BINI
Prior Surgery	Baseline Characteristic / Potential Confounder	Columbus trial data; Flatiron EHR	A binary variable indicating whether patients previously used surgery to reduce/remove tumors as a form of treatment
Prior Radiotherapy	Baseline Characteristic / Potential Confounder	Columbus trial data; Flatiron EHR	A binary variable indicating whether patients underwent radiotherapy among those receiving prior systemic therapy

Prior Immunotherapy	Baseline Characteristic / Potential Confounder	Columbus trial data; Flatiron EHR	A binary variable indicating whether patients underwent immunotherapy among those receiving prior systemic therapy
---------------------	--	-----------------------------------	--

#### 8.4. Data sources

##### COLUMBUS trial

COLUMBUS was a two-part, multicenter, randomized, open-label, Phase 3 clinical trial. Part 1 of the trial investigated the effectiveness and safety of three treatment regimens in patients with locally advanced unresectable or metastatic BRAFV600-mutant metastatic melanoma who were treatment naïve or whose cancer had progressed after 1L IO. In Part 1 of the trial, patients were randomized to one of three treatment arms: 1) 450mg once daily encorafenib and 45mg twice daily binimatinib (n=192), 2) 960mg twice daily vemurafenib (n=191) and 3) 300mg once daily encorafenib (n=194). Randomization was stratified by AJCC disease stage (IIIB, IIIC, IVM1a, IVM1b, or IVM1c), ECOG performance status (0, 1), and BRAFV600 mutation profile (V600E, V600K). Progression-free survival was the primary endpoint in the trial, while OS was one of the secondary endpoints. Patients were enrolled in Part 1 of the trial between 30 December 2013 through 10 April 2015.

The ENCO+BINI arm of Part 1 of the trial will be used in this study (database lock date: 15 September 2020). Part 2 of the trial compared encorafenib 300mg once daily plus binimatinib 45mg twice daily versus encorafenib 300mg once daily alone and will not be considered.

##### Flatiron Health EHR

The Flatiron Health EHR database is a longitudinal, de-identified real-world database derived from EHRs collected in US cancer clinics. The database covers more than 2.6 million active cancer patients treated at over 800 sites of care across 4 US census regions. Patient-level data includes both structured (diagnosis, demographics, laboratory values, biomarker information, drug orders, visits, etc.) and unstructured (physician notes, radiology, and pathology reports, etc.) sources. Data on death is drawn from structured or unstructured data fields in the EHR, and publicly available sources of mortality including the US Social Security Death Index, and commercial obituary data.

Pfizer has contracted with Flatiron for a custom data extract containing information on patients with advanced melanoma who received treatment with ENCO+BINI. A cohort of ENCO+BINI patients meeting the eligibility criteria defined for this study will be obtained from this custom data extract as described in [Section 8.2](#) and used in all analyses.

#### 8.5. Study size

The number of patients eligible for the study will be determined in accordance with the sample selection conducted per the criteria described in [Section 8.2](#).

#### 8.6. Data management

Clean, patient-level datasets for COLUMBUS and Flatiron Health data will be generated for use throughout the study. This process will entail basic exploratory checks to ensure data integrity;

cleaning and reformatting the raw data as needed; and creating variables for all key study measures. All data will be stored and maintained on a secure encrypted non-cloud-based server and accessed over a secure internal private wide area network. The data will be made accessible only to individuals working on the current study. No attempt will be made to identify individual patients, hospitals, or physicians. Analyses will be conducted using SAS version 9.4 and/or R version 4.1.0 or later

## 8.7. Data analysis

### 8.7.1. Analysis of baseline characteristics

Patient baseline characteristics at or prior to the index visit will be summarized for ENCO+BINI groups from both data sources. Patient characteristics to be summarized will be based on availability in both data sources and clinical input. A list of characteristics expected to be summarized is provided in [Table 1](#).

Baseline characteristics will be summarized at the index date if measured at that time. In the Flatiron data, for baseline characteristics that are not measured at the index date, the closest available measure to the index date within a baseline period will be used. The **baseline period** will be defined as a time window ranging before and potentially shortly after (e.g., ~3 months prior to ~1 month after) the index date. Different durations of the time window will be considered to maximize data availability on baseline characteristics; specific durations will be selected based on data availability and guided by clinical input.

Patient baseline characteristics will be summarized descriptively using mean (with standard deviation) and median (with interquartile range) for continuous variables and count (with proportions) for categorical variables. Missingness for each baseline characteristic (at the index date or within the baseline period) will also be summarized.

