#### 8.2.1. Inclusion criteria

Inclusion criteria are provided separately for the 2 data sources below. Key inclusion criteria in the COLUMBUS trial were:

- Histologically confirmed diagnosis of locally advanced, unresectable, or metastatic cutaneous melanoma or unknown primary melanoma

- American Joint Committee on Cancer (AJCC) disease stage of IIIB, IIIC, IVM1a, IVM1b, or IVM1c at trial enrolment
- Presence of BRAF V600E or V600K mutation in tumor tissue prior to enrollment
- At least 18 years of age at randomization
- Eastern Cooperative Oncology Group (ECOG) status of 0 or 1 at randomization
- Treatment naive or had progressed on or after previous first-line (1L) immunotherapy at randomization

Patients from the COLUMBUS trial included in this analysis will be those patients:

- Randomized to ENCO+BINI arm of the trial to receive 450mg once daily encorafenib and 45mg twice daily binimatinib combination therapy, and
- With available data on mortality

Pfizer has contracted with Flatiron for a custom data extract containing information on patients with advanced melanoma. Key inclusion criteria from the COLUMBUS trial will be applied to the Flatiron RWD population to align the populations to the extent possible between the 2 data sources.

Eligibility criteria applied to the Flatiron custom data extracted received by Pfizer included:

- Diagnosis of melanoma (International Classification of Diseases 9th or 10th Revision Clinical Modification - ICD-9-CM: 172.X; ICD-10-CM: C43.x) and secondary malignancy or metastasis (ICD-9-CM: 196.x, 197.x, 198.x; ICD-10-CM: C77.x, C78.x, C79.x).
- Confirmed BRAF V600E/V600K activating mutation reported in the data based on laboratory or genetic analysis results.
- At least 1 order or administration of ENCO+BINI treatment after the diagnosis of metastatic melanoma and within the available data cut period (01 January 2011 to 01 January 2022)
- Order or administration of ENCO+BINI treatment at least 3 months prior to the data cutoff date (e.g., 01 October 2022)

The sample of patients from the Flatiron health EHR data for this study will be identified using the following additional criteria applied to the custom data cut received from Flatiron:

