- At least 1 order or administration of ENCO+BINI treatment after the diagnosis of metastatic melanoma and after 27 June 2018 (FDA approval date for ENCO+BINI for use in patients with metastatic melanoma); the date of the first such order or administration of ENCO+BINI will be taken as the **index date**.
- At least 18 years of age at the index date
- Treatment-naive or had previous 1L IO at index date, based on review of medication orders or administration prior to the index date.
- ECOG status of 0 or 1 at the index date

- With available data on mortality

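### The timing of real-world ECOG is stated inconsistently, so a value recorded after survival time zero could decide Flatiron eligibility, and a post-index ECOG or LDH could enter the Cox model; the expected effect is small and the repair cheap

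*Combined protocol and SAP*

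**What the plan says.** For Flatiron patients the index date is defined in section 8.2.1: "the date of the first such order or administration of ENCO+BINI will be taken as the" index date. Survival runs from there; section 8.3, Table 1 says "In Flatiron EHR, defined as the time from the index date to the date of death", and section 8.7.2 repeats it.

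ECOG timing is given in several places:

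- **Section 8.2.1, Flatiron inclusion:** "ECOG status of 0 or 1 at the index date".
- **Section 8.2.1, COLUMBUS inclusion:** "Eastern Cooperative Oncology Group (ECOG) status of 0 or 1 at randomization".
- **Section 8.2.2, exclusion for ECOG ≥2:** "at the time of randomization for patients from COLUMBUS, during the baseline period for patients in Flatiron EHR".
- **Section 8.3, Table 1:** the ECOG and LDH rows are labelled as index values, but their Flatiron definitions refer to the baseline period. LDH in COLUMBUS is taken at trial baseline.
- **Section 8.7.1:** the opening sentence limits baseline characteristics to values no later than the index visit. The next paragraph takes the index-date value if there is one. For Flatiron patients without one, it takes the nearest value in a baseline period running "before and potentially shortly after (e.g., ~3 months prior to ~1 month after) the index date". The window length is left open, to be chosen on data availability and clinical input.

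Section 8.7.4 lists ECOG, LDH and BMI among the expected Cox adjustment factors. Section 8.7.3 expects substantial missingness in ECOG and LDH.

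**The concern.** A value measured after time zero exists only for someone still alive and under observation, and it may reflect what happened after follow-up began. If it decides who is in the Flatiron cohort, that cohort is selected partly on early outcome, while COLUMBUS was selected at randomization. Excluding Flatiron patients who deteriorated soon after index would flatter the real-world survival curve. Admitting patients who improved soon after index would do the opposite. A post-index LDH used as a baseline covariate could move the adjusted hazard ratio either way.

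There is also a plain reproducibility problem. Two analysts could build different Flatiron cohorts from the same text, and the primary comparison rests on that cohort. No analysis restricted to values on or before index is planned that would show the difference.

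**Working it through.** **1. The rules applied to one patient.** Take a Flatiron patient with no ECOG on the index date, an ECOG of 1 some time before it, and an ECOG of 2 sooner after it.

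- Section 8.2.1 read literally: no index-date value, so eligibility cannot be settled.
- Opening sentence of 8.7.1: ECOG 1, eligible.
- Section 8.2.2 with the closest-value rule of 8.7.1 and a post-index tail: ECOG 2, excluded.
- The same rule without a tail: ECOG 1, eligible.

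The same closest-value rule selects the LDH and BMI that enter the Cox model. LDH appears in no inclusion or exclusion criterion, so it acts only there.

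**2. Inputs for size.** The plan gives no figure to reproduce; section 8.5 states no sample size.

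- *From the documents:* 192 COLUMBUS patients; enrolment 30 December 2013 to 10 April 2015 and lock 15 September 2020, hence 65 to 80 months of follow-up; Flatiron index dates after 27 June 2018.
- *Flatiron follow-up, assumed.* Section 8.2.1 gives both "within the available data cut period (01 January 2011 to 01 January 2022" and "at least 3 months prior to the data cutoff date (e.g., 01 October 2022", so three ranges were used: A 3–42, B 9–51, C 3–51 months.
- *Also assumed:* 250 Flatiron patients, exponential survival with median 24 months, true hazard ratio 1, equal deterioration in both cohorts, exclusion only if alive at 2 weeks, no loss to follow-up. Loss to follow-up would lower deaths and raise the standard error.

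Hazard ratios are COLUMBUS versus Flatiron; above 1 favours Flatiron. The standard error of the log hazard ratio is 0.132 (A), 0.122 (B) and 0.125 (C). With 100 Flatiron patients it is 0.16–0.18.

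**3. Main case: the closest value decides exclusion.** Let q be the fraction deteriorating to ECOG ≥2 (3–5%), r their hazard multiple (2–3), and f the fraction whose nearest value is post-index (10–30%).

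- Expected exclusions, 250 × f × q: 250 × 0.10 × 0.03 = 0.75 to 250 × 0.30 × 0.05 = 3.75, about 1 to 4 patients.
- Hazard ratio at time zero, with m = 1 + q(r − 1) and p = qf: m(1 − p)/(m − pr).
  - Low: 1.03 × 0.997/(1.03 − 0.006) = 1.003.
  - High: 1.10 × 0.985/(1.10 − 0.045) = 1.027.
- The high-risk patients die early, so the hazard ratio over the whole follow-up is smaller. Large-sample simulation with paired Cox fits gives 1.002–1.015 (A) and 1.002–1.013 (B and C). A repeat simulation agreed within 0.001.
- In standard errors: ln(1.015)/0.132 = 0.0149/0.132 = 0.11.

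**4. Opposite flow.** If 0.5–2% of Flatiron patients, with 1.5–2 times the hazard, are admitted after improving, the hazard ratio is 0.998–0.986. The larger is ln(0.986)/0.132 = −0.11 standard error.

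**5. Post-index LDH in the model.** Assume a log-hazard of 0.4 per SD and a half-SD shift in 10–30% of Flatiron patients. A rough value is exp(± fraction × 0.5 × 0.4), or exp(±0.02) to exp(±0.06). Simulated results are 0.982–0.946 for a downward shift and 1.022–1.065 for an upward one. The largest is ln(1.065) = 0.063, about 0.48 standard error under A (0.063/0.132) and about 0.52 under B (0.063/0.122).

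**6. What a strict pre-index-only rule could do.** Suppose patients whose only ECOG is a post-index ≥2 are kept, and 1–5% of the Flatiron cohort were truly ≥2 at index with 1.5–3 times the hazard. The unadjusted hazard ratio is then 0.995–0.948. ln(0.948) = −0.053, which is 3.6 times the main-case maximum of 0.015.

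**The case against.** The best defence is that section 8.7.1 defines the baseline period and gives an order of choice, and that section 8.2.2 and Table 1 merely use the defined term. Table 1 labels the row as an index value and then defines it over the baseline period, so the window can be read as the working meaning of 'at index'. Much of this stands: the sections are not all independent rules. It does not remove the clash between 8.7.1's opening sentence and its own window, or the different wording of 8.2.1 and 8.2.2.

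Second, the post-index tail is only a possibility, given as an example. That stands. A reader might infer that the plan has committed to post-index values; it has not.

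Third, data availability is a legitimate aim given the missingness expected in section 8.7.3, and a strict pre-index-only rule has its own bias (step 6). That stands too, and it is why the fix does not discard post-index values outright.

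Three stronger readings are tempting and unsupported:

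- *Any ECOG ≥2 in the window excludes.* Section 8.2.2 does not rule this out, but the closest-value rule more naturally yields one value per patient. The corresponding bound (hazard ratio about 1.02–1.05, up to 0.38 standard error) should carry no weight.
- *LDH decides eligibility.* No criterion uses it.
- *Every post-index value is on-treatment.* The index date can be an order date, so some may precede the first dose. They still follow time zero.

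**Conclusion.** The point holds as an inconsistency in the text with a conditional, small consequence. If a post-index tail is adopted, information from after time zero can decide ECOG eligibility in the Flatiron cohort alone, and a post-index ECOG or LDH can enter the adjusted model. Without a tail the effect is zero and only the conflicting wording remains.

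The documents determine neither size nor net direction. On the assumptions above, the main eligibility effect is about 0.1 standard error, and the most extreme LDH setting reaches about half a standard error. A reader might infer a material bias in favour of real-world survival; the documents do not support that, because the flows run both ways and the deterioration rates, hazard multiples, LDH shift and Flatiron sample size are all assumed. This is a minor, cheap improvement, justified by the ambiguity in cohort definition rather than by a large expected bias.

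**What to change.** Before outcomes are examined, reconcile sections 8.2.1, 8.2.2, 8.3 (Table 1) and 8.7.1 to one rule:

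1. One selected ECOG value per Flatiron patient decides eligibility.
2. For ECOG, LDH and BMI, use the closest value on or before the index date within the window whenever one exists, even if a post-index value is nearer.
3. For patients whose only value in the window is post-index, prespecify one handling (use it, or treat it as missing and impute) and run the other as a labelled sensitivity analysis.
4. Run the survival comparison with and without patients whose only ECOG is post-index.
5. Report how many Flatiron patients have only a post-index ECOG, how many of those are ≥2, and how many change eligibility or covariate value between rules.

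The cost is SAP wording, a few counts and a few extra runs. Some values used will be older than the nearest post-index one. Missingness rises only if post-index-only values are treated as missing. Keeping patients whose only ECOG is a post-index ≥2 carries its own bias; the documents cannot say whether such patients were already ≥2 at index, and the runs in item 4 show how much it matters.

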### 8.7.2. Unadjusted comparison of OS between ENCO+BINI cohorts in Columbus trial versus in Flatiron RWD

OS will be summarized for ENCO+BINI cohorts in the Columbus trial and Flatiron RWD. In the Columbus trial, OS will be defined as the time from the date of randomization to the date of death due to any cause; if death was not observed, patients will be censored at the date of last contact or the data analysis cutoff date whichever occurs first. In Flatiron RWD, OS will be defined as the time from the index date to the date of death; patients without a date of death will be censored at their last known activity date (e.g., the last clinical note date) or the end of the follow-up period whichever occurs first.

An unadjusted comparison of OS with ENCO+BINI in the Columbus trial versus in Flatiron RWD will be conducted using Kaplan-Meier (KM) analyses. OS over time in these 2 cohorts will be plotted and compared using a log-rank test, with median survival time and survival proportions reported at selected time points (e.g., 6 months, 1 year, 2 years). A hazard ratio for OS comparing ENCO+BINI in Columbus trial versus in Flatiron RWD will be estimated based on a univariable

Cox proportion hazards model. The proportional hazards assumption will be assessed using tests of Schoenfeld residuals.

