**NON-INTERVENTIONAL (NI) STUDY PROTOCOL**

**Study information**

Title	Overall survival (OS) in patients with metastatic BRAFV600-mutant melanoma treated with encorafenib plus binimatinib in the COLUMBUS trial versus in real-world practice data
Protocol number	C4221035
Protocol version identifier	1.0
Date	24 February 2023
Active substance	Encorafenib plus Binimatinib
Medicinal product	Braftovi® plus Mektovi®
Research question and objectives	
The study objective is to describe and compare OS in patients with metastatic BRAFV600-mutant melanoma treated with encorafenib plus binimatinib (ENCO+BINI) in the Phase 3 COLUMBUS clinical trial versus in real-world data (RWD) from Flatiron Health.
 
This study will help contextualize real-world clinical effectiveness of ENCO+BINI and assess the suitability of pooling clinical trial and RWD on ENCO+BINI from these two sources for use in future real-world studies.

Author(s)	PPD , PharmD PPD

This document contains confidential information belonging to Pfizer. Except as otherwise agreed to in writing, by accepting or reviewing this document, you agree to hold this information in confidence and not copy or disclose it to others (except where required by applicable law) or use it for unauthorized purposes. In the event of any actual or suspected breach of this obligation, Pfizer must be promptly notified.

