There is increasing interest in using real-world data (RWD) to evaluate effectiveness of encorafenib plus binimatinib (ENCO+BINI). One important use of the emerging RWD for ENCO+BINI is to assess how clinical effectiveness in real-world practice compares to efficacy observed in clinical trials. Clinical trial data (CTD) and real-world data on ENCO+BINI may also be pooled to provide a larger sample size for future evidence generation studies, provided outcomes are sufficiently consistent between CTD and RWD settings.

However, use of RWD presents important challenges. In general, differences in baseline characteristics between patients enrolled in clinical trials and patients receiving treatment in RWD settings can result in bias. While this concern can be mitigated with adequate statistical adjustment, missing data in RWD sources on key confounders of outcomes may also hamper ability to adjust for such baseline differences. Suitability of RWD for specific uses therefore needs to be assessed on a case-by-case basis considering details of the RWD data source and outcomes of interest.

In this study, we will compare overall survival (OS) between patients receiving ENCO+BINI in the Phase 3 COLUMBUS trial versus in the Flatiron Health Electronic Health Records (EHR) database. Baseline profiles of patients will also be compared across these settings to characterize differences in patients receiving ENCO+BINI and adjustments will be made for differences in baseline factors associated with OS. Missingness for key baseline characteristics will be addressed using a multiple imputation approach that has been validated for Flatiron Health EHR data in metastatic melanoma. This study will help contextualize real-world clinical effectiveness of ENCO+BINI, and assess the

suitability of pooling CTD and RWD on ENCO+BINI from these 2 sources for use in future RWE studies.

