## 7. RESEARCH QUESTION AND OBJECTIVES

### Primary Objective

To compare OS between patients with metastatic BRAFV600-mutant melanoma initiating ENCO+BINI in the COLUMBUS Phase 3 trial versus Flatiron Health real-world practice data.

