#### **8.7.4. Adjusted analysis of OS between ENCO+BINI cohorts in Columbus trial versus in Flatiron RWD**

Finally, an adjusted comparison of OS between ENCO+BINI cohorts in the Columbus trial and Flatiron RWD will be conducted. Hazard ratios will be estimated based on a multivariable Cox proportional hazard model, adjusting for key baseline characteristics known or expected to be related to OS in metastatic melanoma (e.g., age, sex, race, body mass index, ECOG performance score, disease stage, LDH, time from diagnosis to metastatic disease, time from metastatic diagnosis to ENCO+BINI initiation and use of prior therapies). Specific adjustment factors listed here may be revised based on expert clinical input.

The adjusted analyses will be conducted using the Columbus trial dataset and each of the RWD datasets with imputed baseline characteristic values in turn. Log-hazard ratios for the difference in OS with ENCO+BINI between the Columbus trial and each imputed dataset will be obtained, and a summary HR obtained by pooling results across all imputed datasets will be generated using Rubin's rules.

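### The plan ties pooling of COLUMBUS and Flatiron data to consistent OS but never says what OS result would count as consistent

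*Combined protocol and SAP*

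**What the plan says.** **Purpose.** The study information table says that the study will help "assess the suitability of pooling clinical trial and RWD on ENCO+BINI from these two sources for use in future real-world studies". Section 6 repeats this and makes pooling acceptable "provided outcomes are sufficiently consistent between CTD and RWD settings". The last limitation in section 8.9 allows that OS comparability between these two sources might be shown by this study, and then cautions that other sources and other outcomes need their own evaluation.

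**Objective.** The primary objective in section 7 is narrower: "To compare OS between patients with metastatic BRAFV600-mutant melanoma initiating ENCO+BINI in the COLUMBUS Phase 3 trial" versus the Flatiron data.

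**Analysis.** In section 8.7.2, "OS over time in these 2 cohorts will be plotted and compared using a log-rank test", with Kaplan-Meier summaries and a univariable Cox hazard ratio. The same section adds: "The proportional hazards assumption will be assessed using tests of Schoenfeld residuals". That is a check of a model assumption and says nothing on whether OS is similar. In section 8.7.4 a multivariable Cox model is fitted to each imputed dataset and "a summary HR obtained by pooling results across all imputed datasets will be generated" by Rubin's rules. Appendix Table 3 shows both hazard ratios with 95% confidence intervals.

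**Size.** Section 8.5 says only: "The number of patients eligible for the study will be determined in accordance with the sample selection". It gives no expected number of deaths and no expected precision.

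None of these places states a margin, an acceptable range for the hazard ratio, or a rule for reading its interval.

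**The concern.** The plan foresees a statement about similarity, but its outputs estimate and test a difference. Failure to reject equal survival may mean that survival is similar, or only that there were too few deaths to tell. An interval that includes 1 has the same ambiguity.

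Without a stated criterion, the judgement of sufficient consistency will be made after the OS result is known. A non-significant result would then be open to being read as support for pooling, and later studies could inherit a pooled dataset on that basis. The intervals in Appendix Tables 2 and 3 will show the imprecision, but nothing says how much imprecision rules out a pooling conclusion.

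**Working it through.** The plan gives no event count, power or margin, so it has no figure of its own to reproduce. The check asks how large a difference could go unnoticed.

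**Input from the documents.** The COLUMBUS encorafenib plus binimetinib arm has n = 192 (section 8.4), so it can contribute at most 192 deaths. Two-sided 5% is inferred from the 95% intervals in the appendix; the plan states no significance level.

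**Formulas.** With D1 COLUMBUS deaths and D2 Flatiron deaths:
- SE(log HR) = √(1/D1 + 1/D2)
- observed HRs that are non-significant: exp(±1.96 × SE)
- probability of missing a true HR h: Φ(1.96 − ln h/SE) − Φ(−1.96 − ln h/SE)

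**Best case.** D1 = 192 and D2 unlimited:
- SE = √(1/192) = 0.0722
- non-significant range: exp(±1.96 × 0.0722) = 0.87 to 1.15
- true HR 1.15: ln 1.15/SE = 0.1398/0.0722 = 1.937; Φ(1.96 − 1.937) = 0.51, and the second term is negligible, so it is missed 51% of the time
- true HR 1.25: 0.2231/0.0722 = 3.092; Φ(1.96 − 3.092) = 0.13, so it is missed 13% of the time

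**Why actual precision will be lower.** Not every COLUMBUS patient need have died and the Flatiron cohort is finite. COLUMBUS deaths that occur after Flatiron follow-up has ended add nothing to the comparison. COLUMBUS follow-up can reach about 6.7 years (30 December 2013 to 15 September 2020). Flatiron follow-up is at most about 3.5 years if it runs from 27 June 2018 to 01 January 2022, the example study end given in Table 1 for PFS. Adjustment and imputation may add variance.

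**Illustration with assumed deaths.** The documents give none of these counts. The last two columns apply an illustrative rule: call the cohorts comparable if the 90% interval lies inside 1/M to M. With c = ln M − 1.645 × SE, that probability is P(|x| < c) for x ~ N(ln h, SE), and 0 if c ≤ 0.

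| Deaths COLUMBUS/Flatiron (assumed) | SE | Non-significant HRs | True HR 1.25 missed | Comparable at true HR 1, range 0.80–1.25 | Comparable at true HR 1.25, range 0.67–1.50 |
|---|---|---|---|---|---|
| 80/40 | 0.194 | 0.68–1.46 | 79% | 0% | 19% |
| 100/60 | 0.163 | 0.73–1.38 | 72% | 0% | 28% |
| 120/100 | 0.135 | 0.77–1.30 | 62% | <1% | 38% |
| 120/150 | 0.122 | 0.79–1.27 | 55% | 14% | 44% |

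The two ranges show the trade-off only; neither is proposed as the right one.

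**The case against.** The strongest reply is that the methods match the stated objective, which is to compare OS. Kaplan-Meier curves, hazard ratios and intervals do that. Pooling is a later use, worded softly, and section 6 says that suitability of real-world data is judged case by case, so the tolerable difference may depend on the future study. The sentence in section 8.9 sits in a caveat whose main job is to limit generalisation. The log-rank test is a descriptive step in a section labelled unadjusted, and neither Appendix Table 2 nor Appendix Table 3 has a place for a p-value.

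Most of this stands. A reader might infer that the plan intends to treat a non-significant log-rank test as proof of comparability. The documents do not support that: no passage says so, and an adjusted hazard ratio with its interval is also planned. Using a log-rank test is not itself the fault. It would also go too far to say that the study will probably miss a material difference, because any such probability beyond the best-case bound rests on death counts that the plan does not give.

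What the reply does not supply is the criterion. Assessing pooling suitability appears in the study's own statement of its research question, and the caveat in section 8.9 limits other sources and outcomes without saying when OS from these two sources is comparable. Case-by-case judgement still needs a stated basis if this study is to inform it.

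**Conclusion.** The concern holds as an omission. The plan attaches a pooling and comparability conclusion to the study without saying what OS result would support it, and neither non-significance nor an interval that includes 1 can fill that gap.

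The size that rests on the documents is the best-case bound: observed hazard ratios of 0.87 to 1.15 would be non-significant, with a 51% chance of missing a true hazard ratio of 1.15. It uses n = 192, a two-sided 5% level and the usual large-sample variance of the log hazard ratio. The table above is illustrative only.

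The planned estimates are unaffected. What is at issue is what may be concluded from them, so this should be fixed before OS is compared.

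**What to change.** 1. In sections 8.7.2 and 8.7.4, state that a non-significant test or an interval including 1 is not evidence of comparability, and that any pooling statement rests on the Rubin-pooled adjusted hazard ratio and its interval.
2. Then choose one of two routes.
   - **(a) Set a criterion.** Before OS is compared, prespecify a hazard ratio range justified on clinical grounds and not fitted to the achievable precision. Conclude comparable only if the 90% interval of the adjusted hazard ratio lies inside it. Give the expected interval width in section 8.5. State that the verdict does not cover the unmeasured differences listed in section 8.9.
   - **(b) Drop the claim.** If no range can be agreed, remove the pooling-suitability wording from the study information table and section 6 and the comparability wording from section 8.9, and report the adjusted hazard ratio with its interval descriptively.

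**Cost.** Both routes need only wording, plus an expected-precision statement under (a); neither needs new data. The sample is fixed, so under (a) a narrow range will often be inconclusive, while a wide one tolerates larger true differences. A comparable label may also reassure more than a non-randomised comparison warrants. Under (b) the study gives up its pooling purpose.
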